### **3.0 Specific Aims and Hypotheses**

Clinically, tibio-talar alignment is assessed through static weight bearing radiographs – however, stance is functionally very different than gait and the tools to capture dynamic bone motion are not readily available in clinical settings. In research, optical motion capture (a technique that uses reflective markers and infrared cameras to track position and motion) is often used to study gait, however its ability to measure dynamic bone motion and position, in this case tibio-talar alignment, is limited. Biplane fluoroscopy is a radiographic technology that can track the talus, and thus measure dynamic ankle alignment. Importantly, some neutrally aligned ankles (determined via static radiographs) may actually exhibit misalignment during gait (dynamic biplane fluoroscopy). Treatment of misaligned ankles with conservative strategies (e.g., wedged insoles) may reduce misalignment, slowing the rate of OA development. We seek to quantify dynamic ankle misalignment in OA patients, detect a possibly hidden dynamically misaligned patient population, and explore how both populations respond to a conservative treatment approach.

**Specific Aim 1:** To investigate ankle kinematics in controls and participants with OA.

**Hypothesis 1:** During gait, there are different tibio-talar kinematics between participants with OA and static varus alignment, participants with OA and static valgus alignment, and controls.

**Specific Aim 2:** To identify dynamically misaligned ankles in participants with OA who are currently classified as neutrally aligned using static analysis.

**Hypothesis 2:** Some participants with OA and static neutral alignment will exhibit varus or valgus tibio-talar misalignment when measured dynamically using biplane fluoroscopy.

**Specific Aim 3:** To evaluate the potential of lateral or medial wedging to restore alignment in participants with OA and misaligned ankles.

**Hypothesis 3:** Participants with OA and static (varus/valgus) tibio-talar misalignment will exhibit reduced misalignment when walking with (lateral/medial) wedge insoles.

**Hypothesis 4:** Participants with OA and static neutral alignment, but with dynamic (varus/valgus) tibio-talar misalignment will exhibit reduced misalignment when walking with (lateral/medial) wedge insoles.

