### **Standing Long Leg X-ray**

If needed, this component will be performed at the VAPSHCS Department of Diagnostic Imaging. Participants will stand still while a frontal X-ray of the hips down is taken. This will allow us to quantify

the alignment at the hip, knee and ankle. We will also take standard foot alignment X-rays, including anterior/posterior and medial/lateral views of the feet.

We will measure the ankle alignment, if a participant is determined to have an ankle alignment type for which the study group is already full, that individual will not be able to participate further in the study, but will be compensated for the visit.

Please note, for participants that do not have a clinical diagnosis of alignment type (those with and without OA), we do not intend to inform them if we note misalignment. It is unknown at this time if ankle misalignment is causative to the development of ankle OA or if it is clinically relevant to prevention or conservative treatment of OA; these are some of the questions that this study hopes to address. Therefore, the information would not be useful to participants.

The CT scan and Biplane Fluoroscope session will be conducted in no particular order and may be conducted over multiple visits.

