### **Additional Analyses:**

1) Ankle misalignment likely varies during gait, and the pose of the foot during peak misalignment may not correlate with the position of the foot in the clinical 2D X-ray. To investigate this, the peak misalignment (varus or valgus) during gait as measured from the talar surface angles and talar tilt in data set 2 will be compared to the peak from the static standing fluoroscopic, this will be done for all groups. The result will be a measure of how frequently current clinical measure captures true maximum misalignment during gait.

2) The methods used to generate data set 2 can be used to re-create any 2D position from the 3D kinematics. Considering additional analysis 1, we may identify a phase of gait that more reliably demonstrates maximum misalignment (e.g. at heel rise). At the peak misalignment during that phase, we will generate additional simulated 2D X-ray images, in perspectives which would be possible to capture diagnostically (e.g. straight AP views and minor variations). In these new views, we will re-measure the talar surface angle and talar tilt. Such an exploration requires no additional subject X-ray exposure, as it is a digital processing of the data already collected. The result may be a 2D X-ray imaging angle / foot pose combination which is better suited than current methods for detecting maximum misalignment. This information may have immediate clinical benefit and will be rigorously pursued with additional study.

3) In a similar vein, we will perform a sensitivity test on the current clinical imaging methods. We will generate a series of 2D X-ray image planes by varying the standard clinical AP X-ray perspective in 1 degree increments about the SI and ML axes. Talar surface angle and talar tilt will be recalculated for each of these perspectives. By replicating this measure over a range of  $\pm 15$  degrees, we will determine the sensitivity of the clinical measure to foot positioning during diagnostic imaging.

The preceding three additional analysis serve to determine: (1) the ability of current methods to determine peak misalignment, (2) if a clinical angle / pose exists that is more diagnostically meaningful, and (3) the sensitivity of positioning to the current clinical method.

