### **Power:**

Our study is powered from a pilot study of ankle alignment during static phases of gait. Refer to Figure 3-6, Left: OA participants (group 1, 30 participants with 3 trials per subject, n=90) vs. Plot 1, Right: controls (group 2, 20 participants with 3 trials per subject, n=60).

Power analysis for coronal plane misalignment: Assumptions: mean = -1.8 degrees SD=1.8 degrees n=90 (30x3) for an OA group, and mean=1.7 degrees, SD=2.9 degrees, n=20 for the controls (valgus or varus) with 3 trials per subject and within subject error of 1.5 degrees. Based on 5000 simulated datasets and performing the mixed regression model described in H1, there is >99% power to detect the difference between groups, i.e., 3.5 degrees, as statistically significant, at p=0.05.

Coronal alignment is the measure that yields ankle varus, neutral or valgus. This demonstrates an appropriate sample size for the effect size of ankle alignment. Additionally, the pilot study did not differentiate between varus or valgus alignment. Due to demographics, it is possible that all six participants were varus or neutral. We suspect that cleaner separation of groups for comparison will only improve our ability to detect significant differences between groups.

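### Additional analysis 1 draws a conclusion about the clinical radiograph without using it, and compares an uncorrected gait peak with a still standing pose, which biases the result toward the static measure missing the peak

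*Combined protocol and SAP*

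**What the plan says.** Section 5.6, Additional Analyses, item 1 takes as its gait quantity "the peak misalignment (varus or valgus) during gait as measured from the talar surface angles and talar tilt in data set 2". This "will be compared to the peak from the static standing fluoroscopic, this will be done for all groups". The stated reading is: "The result will be a measure of how frequently current clinical measure captures true maximum misalignment during gait". The summary after item 3 gives the purpose of item 1 as establishing "the ability of current methods to determine peak misalignment".

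Section 3.0 says what the clinical method is: "Clinically, tibio-talar alignment is assessed through static weight bearing radiographs". Section 5.5, Standing Long Leg X-ray, describes the radiograph taken in this study when no usable image exists: "Participants will stand still while a frontal X-ray of the hips down is taken". Hypothesis 2 in section 5.6 uses that standing radiograph as its static measure. Standing fluoroscopy is a separate acquisition, described under Biplane Fluoroscopy – Baseline. It is done on the laboratory walkway in lab shoes, and possibly also with a neutral insert or barefoot.

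The only error figure is in the Power section, for coronal alignment: "with 3 trials per subject and within subject error of 1.5 degrees". Item 1 does not state the number of trials or frames that enter the gait peak, the number of standing images, how far apart two values may be and still agree, or any handling of measurement error. Data set 2 is not defined in the text available for review.

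**The concern.** The comparator and the conclusion do not match. Item 1 measures stance against gait within one imaging system, but reports the answer as the performance of a different measure, the clinical radiograph. Differences between the two static images in footwear, projection, date and technique would go unexamined.

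The two sides also respond differently to error. The largest of several noisy values lies above the underlying value on average, and a single still pose has no such upward pull. With no rule for when the static value counts as capturing the peak, part of the reported miss frequency would be measurement error presented as a real dynamic change. The comparison as written cannot separate the two. At stake is a published statement that standing images often fail to show the true maximum, in a study whose stated hope is to improve on the current clinical examination.

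**Working it through.** **The plan's own figure.** Item 1 has no numerical target. The only computed design figure is the power for Hypothesis 1, and it reproduces. With SDs 1.8 and 2.9, 30 and 20 participants, 3 trials and error 1.5:

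- Trial error variance of a participant mean = 1.5²/3 = 0.75.
- SE = √[(1.8² + 0.75)/30 + (2.9² + 0.75)/20] = √(0.133 + 0.458) = 0.769.
- Power = Φ(3.5/0.769 − 1.96) = Φ(2.59) = 99.5%, two-sided 0.05. The plan says above 99%.

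The 3 trials and 1.5 degrees are therefore taken at face value below.

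**Gait peak against one static value, no true difference.** Let k be the number of gait values. Assume independent normal errors with SD 1.5 on both sides.

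- The k gait values and the static value are exchangeable, so P(gait peak > static) = k/(k+1). At k = 3 this is 75%.
- Mean excess = 1.5 × E(maximum of 3 standard normals) = 1.5 × 3/(2√π) = 1.5 × 0.846 = 1.27 degrees.
- By simulation at k = 3, static lies within 1 degree of the peak in 34% of participants and within 2 degrees in 62%.
- If the peak is taken as an absolute angle, the exceedance is still 75%. The mean excess is 0.8 degrees for a true angle of 0 and 1.1 degrees for a true angle of 1.8.

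**Sensitivity to what the plan leaves open (simulation; assumed inputs marked).**

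| Setting | Gait exceeds static | Mean excess (degrees) |
|---|---|---|
| k = 3, error 1.5, one static value | 75% | 1.3 |
| k = 10 independent values (assumed) | 91% | 2.3 |
| k = 30 independent values (assumed) | 97% | 3.1 |
| k = 10, static peak of 3 values (assumed) | 77% | 1.0 |
| k = 3, static peak of 3 values (assumed) | 50% | 0.0 |
| k = 3, error 0.5 (assumed) | 75% | 0.4 |
| k = 3, error 1.5, true gait 2 degrees below standing (assumed) | 35% | not tabulated |

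The k = 10 and k = 30 rows treat frames as independent with the trial-level error. Correlated frames behave like a smaller k.

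**Does the fix work?** Tolerance = 1.96 × √2 × 1.5 = 4.16, about 4.2 degrees. Simulated with no true difference:

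| Gait summary | Exceeds static at all | Exceeds by more than 4.2 degrees |
|---|---|---|
| Raw maximum, k = 3 | 75% | 6% |
| Raw maximum, k = 10 | 91% | 14% |
| Raw maximum, k = 30 | 97% | 25% |
| Peak of 3-trial average curve, 10 independent frames | 80% | 4% |
| Peak of 3-trial average curve, 30 independent frames | 87% | 6% |

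Averaging alone leaves 80% to 87% exceedance. Averaging with the tolerance brings false misses to about 4% to 6%.

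The tolerance has a price. If every gait value truly lay 3 degrees above standing, the rule would count a miss in about 54% of participants with 10 independent frames (averaged over 3 trials), and in about 25% with a single averaged value.

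**The case against.** - **Both sides are called a peak.** This is true: the text says the gait peak "will be compared to the peak from the static standing fluoroscopic" peak. One static value is an inference from a participant standing still, and the number of standing images is not given. With equal numbers of values on both sides the bias vanishes. It returns whenever the gait side has more values, which is likely but not documented.
- **The outcome is not fixed in advance.** A reader might infer that static imaging must miss the peak by construction. The documents do not support that. The k/(k+1) result needs a zero-tolerance rule, which the plan does not state, and no true difference. If gait were truly 2 degrees less misaligned than standing, gait would exceed static in only 35% at k = 3. With an error of 0.5 degrees, static would be within 2 degrees of the peak in 99%.
- **The larger figures are not the plan's.** Only k = 3 with 1.5 degrees uses its numbers. That error is stated for coronal alignment, not per frame and not for talar tilt or talar surface angle.
- **The comparator has merit.** Standing and walking fluoroscopy share one system and isolate stance against gait. Retrieved radiographs may be old or from other sites, and Hypothesis 2 already sets the radiograph against dynamic classification. A reader might infer that the study never tests the radiograph, and that is wrong. It is also possible that data set 2 includes a simulated clinical view. These points justify keeping standing fluoroscopy. They do not justify reporting its result as that of the clinical measure.
- **Effect on item 2.** A reader might infer that an inflated miss rate drives the search for a better view. Item 2 depends mainly on the phase at which the peak occurs, and its findings are to be followed by further study.
- **Control benchmark.** Running item 1 in every group already implies a control rate. What is missing is its use as the yardstick.

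**Conclusion.** The point holds in two parts. First, item 1 attributes its result to the clinical measure, which section 3.0 identifies as the static weight-bearing radiograph, while comparing against standing fluoroscopy. This rests on the text alone. Second, an uncorrected gait peak is not the true maximum, and the frequency is biased toward a static miss. On the plan's 3 trials and 1.5 degree error this is about 75% exceedance and 1.3 degrees on average when nothing truly differs. That assumes one value per trial, a peak pooled over trials, one static value and independent normal errors.

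The size for this study cannot be fixed, because the numbers of gait and standing values, their correlation, and the error of talar tilt and talar surface angle are not stated. Part of any observed excess may be the genuine dynamic change being sought. Item 1 is secondary and descriptive. Hypotheses 1 to 4 and the stated power are untouched, and the priority is low.

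**What to change.** Amend item 1 as follows.

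1. For the conclusion about the clinical measure, use the standing radiograph already collected or retrieved. Keep standing fluoroscopy as a second, same-modality comparison, labelled as stance versus gait.
2. State how many trials and frames enter the gait peak and how many standing images give the static value. Average trials within participant and take the peak of the averaged curve.
3. Define a miss as a gait peak exceeding the static value by more than a tolerance derived from the study's own repeat-trial error for talar tilt and talar surface angle. If the 1.5 degree figure applied, this would be about 4.2 degrees. Averaging without the tolerance is not enough.
4. Report the OA miss rates beside the control rate and interpret them against it.
5. Replace the reference to the true maximum with the measured peak, and say that error contributes to it.

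The cost is analysis wording and some programming on existing data, with no added exposure. The downsides are that averaging and the tolerance can hide a small or brief true peak, and that retrieved radiographs may differ in date and technique. Showing the full distribution of gait-minus-static differences beside the miss rate would limit the first of these.

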## **5.6 Data Analysis**

### **Plan and Hypotheses:**

Hypothesis 1: During gait, there are different tibio-talar kinematics between OA participants with static varus alignment, OA participants with static valgus alignment, and controls.

Linear mixed effects regression will be used to test for differences in gait kinematic measures coronal plane alignment being the primary dependent variables by OA group (clinical OA varus, clinical OA valgus or controls, the independent fixed effects). Study subject will be modeled as a random effect. If the omnibus test for association between gait kinematic measure and OA group is significant, then pair-wise comparisons will be carried out.

Hypothesis 2: Some static neutrally aligned OA participants will exhibit varus or valgus tibio-talar misalignment when measured dynamically using biplane fluoroscopy.

To determine the potential miss-categorization of OA neutrally aligned participants: frequencies, percentages and 95% confidence will be estimated for the number of participants in the OA static (from standing radiograph) neutral group who are classified into varus, valgus or neutral using dynamic measures (from fluoroscopy trials).

Hypothesis 3: OA participants with static (varus/valgus) tibio-talar misalignment will exhibit reduced misalignment when walking with (lateral/medial) wedge insoles.

Linear mixed effects regression will be used to test for improvement in misalignment, i.e. the reduction in coronal plane disparity between OA and control participants (the dependent variable) when walking with a wedge vs. no wedge (the independent fixed effect) for OA varus and OA valgus participants separately. Subject and subject-x-wedge interaction (the latter to account for variability across multiple trials in the difference in within subject misalignment by wedge use) will be modeled as random.

Hypothesis 4: OA participants with static neutral alignment, but with dynamic (varus/valgus) tibio-talar misalignment will exhibit reduced misalignment when walking with (lateral/medial) wedge insoles.

This will be tested using the same methods as Hypothesis 3, substituting OA varus and valgus participants (from static radiographs) to those who are neutral in static radiography, yet varus or valgus dynamically.

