4) Transverse alignment of the ankle joint is technically more challenging to diagnose due to the need of such an superior / inferior image to pass through the tibia. With the methods described above, we can perform these measurements without difficulty. Using a similar regression and criteria as in Hypothesis 1, we will evaluate differences in transverse plane alignment during gait. Additional measures will compare the changes in malleolar / talar dome side spacing and the closest approach of the transverse borders of the malleoli to the talus. This may identify abnormal transverse wear patterns within the ankle joint – a measure that will not only benefit prevention, but that has significance in ankle replacement.

5) We will use a similar regression as in Hypothesis 1 to determine if there are differences in gait kinematic measures between OA varus / valgus (from static radiograph) and OA varus / valgus (from fluoroscopy trials). This will indicate whether these groups exhibit similar kinematics during gait, despite different static diagnostic determination.

6) We may find participants who do not benefit from wedge insoles (non-responders), depending on both the presence and size of these subgroups; this will yield pilot data to support identifying and investigating these subgroups in follow up proposals.

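### Additional analysis 5 tests gait coronal alignment between one group selected on that measure and one selected on the static film, so its coronal contrast cannot show whether the groups move alike

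*Combined protocol and SAP*

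**What the plan says.** Section 5.6, Additional Analyses, item 5, sets out the comparison: "We will use a similar regression as in Hypothesis 1 to determine if there are differences in gait kinematic measures between" the two sets of OA ankles, namely "OA varus / valgus (from static radiograph) and OA varus / valgus (from fluoroscopy trials"). It then states what the result is for: "This will indicate whether these groups exhibit similar kinematics during gait, despite different static diagnostic determination".

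Three other places in section 5.6 fix what this means:

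- **Outcome.** The Hypothesis 1 regression that item 5 borrows has "gait kinematic measures coronal plane alignment being the primary dependent variables".
- **Formation of the fluoroscopy group.** Under Hypothesis 2, static-neutral OA participants are "classified into varus, valgus or neutral using dynamic measures (from fluoroscopy trials"). Hypothesis 4 describes those who change class as "those who are neutral in static radiography, yet varus or valgus dynamically".
- **Classifying measure.** The Power section says: "Coronal alignment is the measure that yields ankle varus, neutral or valgus".

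The static groups come from a different source. Section 5.5, under eligibility screening and group determination, assigns them from the medical record diagnosis and/or x-ray measurement.

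The plan gives no gait cut-off, no separate set of trials for classification, no adjustment for how the groups were formed, and no restriction of item 5 to measures other than the classifying one.

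**The concern.** Every ankle in the fluoroscopy-defined group lies beyond the gait cut-off because that is how it entered the group. An ankle in the static group has to be beyond the cut-off only on the static film or in the chart; in gait it may lie anywhere. Comparing the two groups on gait coronal alignment compares a distribution truncated on the outcome with one that is not. The expected gap then depends on the cut-off, the spread of angles and how closely gait follows the static film, even if both groups come from one population with one gait pattern.

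What is at stake is how the hidden group sought in Aim 2 is interpreted. Item 5 is where the plan asks whether dynamically detected misalignment resembles the clinically diagnosed kind. A coronal p-value in either direction would be taken as the answer.

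**Working it through.** **1. The plan's own figure.** The only power statement is for OA against controls: means -1.8 and 1.7 degrees, SDs 1.8 and 2.9, 30 and 20 participants, 3 trials each, within-subject error 1.5, difference 3.5 degrees, power above 99%. With balanced trials the random-intercept model reduces to a t-test on participant means, each with error SD 1.5/√3 = 0.87. Over 5,000 simulated datasets this gives 99.6%, so the figure reproduces. It does not bear on item 5, for which no power is given.

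**2. Inputs for the selection check.**

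- Cut-offs: below 90 varus, 100 or above valgus, from the 406-ankle study cited in the Introduction. That study is static; using the same cut-offs in gait is an assumption.
- Spread, first choice: a normal curve fitted to that study's 55/37/8 split. (90 - μ)/σ = 0.1257 and (100 - μ)/σ = 1.4051, so σ = 10/1.2794 = 7.82 and μ = 90 - 0.1257 × 7.82 = 89.02.
- Spread, second choice: the Power section's SDs of 2.9 and 1.8, keeping the mean at 89.02.
- Gait angle = static angle + N(0, s), with s = 0, 2, 4 or 6 degrees (assumed). Measured gait = gait angle + N(0, 0.87).
- No group has its own gait pattern.

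**3. Varus-side gap.** Gap = mean measured gait angle in static-neutral ankles with measured gait below 90, minus the mean in static-varus ankles. Positive means the fluoroscopy group is less varus. Four million simulated ankles per cell:

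| Between-subject SD | s = 0 | s = 2 | s = 4 | s = 6 |
|---|---|---|---|---|
| 7.8 | +6.1 | +5.2 | +4.0 | +2.6 |
| 2.9 | +2.2 | +1.3 | -0.1 | -1.6 |
| 1.8 | +1.3 | +0.4 | -1.1 | -2.6 |

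For example, with SD 7.8 and s = 0 the means are 89.5 and 83.4. With SD 7.8 the valgus-side gaps (positive means the fluoroscopy group is less valgus) are 3.0, 2.2, 1.1 and -0.2.

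**4. Second check, with correlation in place of shift.** Static and gait angles share one mean and one SD (1.8 or 2.9), the cut is 1.8 or 2.9 degrees from the centre, and the static-gait correlation ρ is assumed. The gap, signed as in step 3, is:

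- ρ = 0: -4.5 to -2.9 degrees
- ρ = 0.5: -2.1 to -1.4
- ρ = 0.7: -1.1 to -0.7
- near zero somewhere between ρ = 0.8 and 0.95, depending on SD and cut
- ρ = 0.95: up to +0.8

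**5. What a test would do.** With 40 static-varus participants and k fluoroscopy-varus participants out of 40 neutrals (k = 2 to 11 in step 4), SE = √(SD_static²/40 + SD_fluoro²/k). For ρ = 0.5, SD 1.8 and cut 1.8: gap -1.40, SE = √(1.83²/40 + 0.83²/7) = 0.43, z about -3.3, chance of p < 0.05 = Φ(3.3 - 1.96), about 91%. Over the grid this approximate chance, with no group-specific gait, is 77% to 100% for ρ up to 0.5, 23% to 53% at 0.7, 3% to 28% at 0.8 to 0.9, and 3% to 52% at 0.95.

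**The case against.** The strongest reply is that selection does not guarantee a coronal difference. A reader might infer that the gap is built in and always makes the static group look worse. The tables do not support that: the gap passes through zero and changes sign. To say that static-neutral ankles must lie just beyond the gait cut-off presumes that gait tracks the static film, which is what Aim 2 sets out to question. This part of the reply stands. It does not rescue the analysis, because selection can then produce a false similarity as well as a false difference.

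A reader might also infer that the selection gap exceeds the 3.5 degree planning difference. That holds on the varus side only with SD 7.8, a value fitted to an outside series, and shift SDs up to 4. With the Power section's own SDs no varus-side gap in the step 3 table reaches 3.5, and none of the valgus-side gaps does. Exclusion criterion 4, on severe instability or deformity, may also limit severity in the static group, though it gives no number. If severity beyond the cut-offs is capped at 10 degrees (assumed), the first three gaps in the SD 7.8 row fall to 3.9, 3.1 and 1.9; capped at 5 degrees, to 1.9, 1.1 and -0.2.

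It would also be too strong to call item 5 uninformative as a whole. It speaks of kinematic measures in the plural, and sagittal and transverse motion are not directly selected on, although measures correlated with the coronal angle could be affected indirectly.

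Finally, that the same trials both classify and compare is an inference from the absence of any separate set. Fresh trials would move the step 4 gaps by only about 0.3 to 1.1 degrees and would not remove the selection.

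**Conclusion.** The point holds for the coronal measure. Gait coronal alignment is both the basis of one group and the primary outcome of the borrowed regression, so neither a significant nor a null coronal result can show whether the groups have similar kinematics. The confounding has no fixed size or sign: about +6.1 to +2.6 degrees with SD 7.8, and +2.2 to -2.6 with SDs of 2.9 and 1.8, for shift SDs of 0 to 6.

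These ranges rest on normality, on the assumed shifts, and on static cut-offs carried over to a three-trial gait mean. They also take the fluoroscopy group to be static-neutral, as Hypothesis 4 words it and as item 5's reference to a different static determination implies. They illustrate what selection can do and do not predict this trial's result.

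The point is minor. Item 5 is an exploratory analysis with no power claim, and none of Hypotheses 1 to 4 rests on it.

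**What to change.** In section 5.6, item 5:

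1. Report gait coronal alignment for the two groups descriptively, without a test.
2. Draw inference only from gait measures not used to classify the groups, for example sagittal and transverse tibio-talar motion.
3. Limit the concluding sentence to those measures.

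Coronal excursion over stance should not be counted as a non-classifying measure by default: if classification turns out to use the peak gait angle, selection acts on excursion too. Restricting the static group or adding a coronal covariate is not needed, and would be hard to support with perhaps 2 to 11 fluoroscopy-varus participants.

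The cost is a few lines of wording, with no change to data collection or sample size. The downside is that item 5 then offers no formal test on the coronal measure.

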### Research Design & Methodology:

Up to 120 participants with ankle OA (up to 40 with varus misalignment, up to 40 with valgus misalignment, up to 40 with neutral alignment) and up to 30 participants without ankle OA will be enrolled. Participants will be men and women, age 18-80 years, who are able to stand and walk for at least one hour without significant difficulty. Participants will undergo a series of radiological measurements including: a standard x-ray from the hips down, a set of x-rays of the legs, a CT scan from the knees down, up to 80 fluoroscopic images while walking or

standing. Participants will do the fluoroscopic trials with and without wedged shoe insoles. The radiological measurements will be used to address the aims outlined above.

At the end of this study we hope to: (1) have a better understanding of ankle arthritis, (2) be able to demonstrate the potential for an improvement upon the current clinical examination for ankle misalignment and/or OA, and (3) provide evidence for, or against, the use of shoe inserts to manage and/or treat ankle misalignment and/or OA. It is hoped that this work will aid future clinicians and researchers in delaying or preventing the onset of ankle OA in at-risk veteran and non-veteran patients.

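### Additional analysis 5 judges similarity between the statically and dynamically misaligned OA groups with a test for difference; a non-significant result would not show similarity, and the stated >99% power does not cover this comparison

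*Combined protocol and SAP*

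**What the plan says.** Item 5 of the Additional Analyses (section 5.6) states its method as follows: "We will use a similar regression as in Hypothesis 1 to determine if there are differences in gait kinematic measures". The groups are given as "between OA varus / valgus (from static radiograph) and OA varus / valgus (from fluoroscopy trials"), and the purpose as: "This will indicate whether these groups exhibit similar kinematics during gait, despite different static diagnostic determination".

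The Hypothesis 1 method it borrows is a mixed regression with an omnibus significance test, followed by pairwise comparisons only if that test is significant. Item 5 adds no margin for similarity, no rule based on a confidence interval, and no power figure.

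Three other places bear on the comparison:

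- **Who is in the dynamic group.** For Hypothesis 4, the dynamically misaligned participants are "those who are neutral in static radiography, yet varus or valgus dynamically". Item 5 does not repeat this restriction.
- **How many there may be.** Enrolment of OA participants is "up to 40 with varus misalignment, up to 40 with valgus misalignment, up to 40 with neutral alignment" (Abstract, Research Design & Methodology). Section 3.0 says only: "Some participants with OA and static neutral alignment will exhibit varus or valgus tibio-talar misalignment when measured dynamically using biplane fluoroscopy".
- **Power.** The single power statement assumes "mean = -1.8 degrees SD=1.8 degrees n=90 (30x3) for an OA group" and "mean=1.7 degrees, SD=2.9 degrees, n=20 for the controls", with 3 trials per subject and a within-subject error of 1.5 degrees. It claims more than 99% power for the 3.5 degree difference between OA and controls.

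**The concern.** A test for difference can support the statement that two groups differ. When it is not significant, it supports only the statement that no difference was shown. Item 5 wants to learn whether the groups are alike, and the method it names has no route to that answer except the absence of significance. If the omnibus gate carries over from Hypothesis 1, a null result would not lead to pairwise comparisons at all.

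This matters because section 3.0 sets out to detect a possibly hidden population with dynamic misalignment, and item 5 is where the plan would say whether that population moves like patients whose misalignment is already recognised on radiograph. If few statically neutral participants turn out to be dynamically misaligned, a finding of similarity could reflect an imprecise comparison rather than similar kinematics.

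**Working it through.** **1. The plan's own power figure.** Inputs from section 5.6, Power: OA SD 1.8 (30 participants), control SD 2.9 (20 participants), within-subject error 1.5, 3 trials each, difference 3.5 degrees, p = 0.05 (taken as two-sided). The SDs are read as between-participant.

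- Pooled between-participant variance: (29 × 1.8² + 19 × 2.9²) / 48 = 5.29, so SD 2.30.
- SD of a participant's mean over 3 trials: √(5.29 + 1.5²/3) = √6.04 = 2.46.
- Standard error: 2.46 × √(1/30 + 1/20) = 0.71. Ratio: 3.5 / 0.71 = 4.9.
- Power: 99.8% by noncentral t. Simulation variants gave 99.3% to 99.98%.

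The stated figure reproduces. It describes 30 OA participants against 20 controls at 3.5 degrees.

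**2. The item 5 comparison.** One direction at a time: 40 static cases against n dynamic cases. The 40 is the enrolment ceiling, so it favours the plan. The value of n is not in the documents. Varus and valgus dynamic cases together cannot exceed 40, so n = 20 in each direction would require every statically neutral participant to be reclassified, split evenly. I take 5 to 10 as the working range and show 20 as a generous case.

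Two participant-mean SDs are used: √(1.8² + 1.5²/3) = 2.0 from the OA value alone, and 2.46 from the pooled value above. Standard error = SD × √(1/40 + 1/n); the 95% CI half-width is the t quantile on 38 + n degrees of freedom times that. Example at n = 5, SD 2.0: 2.0 × √(0.025 + 0.2) = 0.95, and 2.02 × 0.95 = 1.9 degrees.

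Power by noncentral t, two-sided 0.05:

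| SD | n | 1 deg | 1.5 deg | 2 deg | 3.5 deg | 95% CI half-width |
|---|---|---|---|---|---|---|
| 2.0 | 5 | 18% | 34% | 54% | 95% | 1.9 |
| 2.0 | 8 | 24% | 48% | 71% | 99% | 1.6 |
| 2.0 | 10 | 28% | 55% | 79% | >99% | 1.4 |
| 2.0 | 20 | 44% | 77% | 95% | >99% | 1.1 |
| 2.46 | 5 | 13% | 24% | 39% | 83% | 2.35 |
| 2.46 | 8 | 18% | 34% | 54% | 95% | 1.9 |
| 2.46 | 10 | 20% | 39% | 62% | 98% | 1.75 |
| 2.46 | 20 | 31% | 59% | 83% | >99% | 1.35 |

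The true differences in the columns are assumptions, except 3.5 degrees, which is the plan's effect size for a different contrast.

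**3. Sensitivity to the reading of the SD.** If 1.8 is a total trial-level SD, the participant-mean SD is √(1.8² − 1.5² + 1.5²/3) = √1.74 = 1.32, and half-widths shrink by about a third. At n = 5 the standard error is 1.32 × √0.225 = 0.63. A 1 degree difference is then 1.6 standard errors, still below the critical value of 2.02, while 1.5 degrees is 2.4 standard errors and would be found more often than not. The size of the problem falls; the logic does not change.

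**4. What an equivalence assessment could deliver.** With no true difference, two one-sided tests at 5% each, SD 2.46 and an assumed margin of ±1.75 degrees (half of 3.5), the chance of showing similarity is 1%, 27% and 65% at n = 5, 10 and 20. At ±2 degrees it is 8%, 47% and 80%. That procedure uses a 90% interval; requiring the 95% interval to fit inside the margin is stricter.

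**The case against.** The strongest reply is that the plan never says a non-significant result will be called similarity. It says the regression will indicate whether kinematics are similar, a mixed model yields an estimate and standard error, and nothing bars reporting an interval. This is one of six additional analyses, and no hypothesis depends on it. A formal equivalence test with so few dynamic cases would mostly be inconclusive. All of that is fair and keeps the point modest. It does not remove it: the named method is a significance test for differences, and nothing else is offered from which similarity could be concluded.

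Two stronger readings are tempting and are not supported.

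- **That the two groups share participants.** Item 5's label for the fluoroscopy group, read alone, could include someone who is varus on both methods. But item 5 itself speaks of groups whose static determination differs, and Hypotheses 2 and 4 apply the dynamic classification to statically neutral participants. The natural reading is that the groups are disjoint and the label merely omits the restriction.
- **That similarity is the likely verdict even when the groups differ.** This depends on the true difference and on n, neither of which the documents give. It holds near 1 degree at every n in the table. At 1.5 degrees it turns on the case: at SD 2.0, power is 48% with 8 dynamic participants and 55% with 10. At 2 degrees with 10 participants, a significant result is the likelier one at either SD (62% or 79%). At 3.5 degrees power is at least 83%. Nor does the plan treat 1.5 degrees as a meaningful difference; there it is a within-subject error.

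**Conclusion.** The concern holds in a limited form. Item 5 puts a question about similarity to a method that can only detect difference, and the >99% power belongs to another contrast. With 5 to 10 dynamic cases against 40, the 95% CI half-width is about 1.4 to 2.35 degrees, so a true difference of up to about 1.5 to 2 degrees could easily go undetected and be taken for similarity. A difference near 3.5 degrees probably would not.

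These figures assume a dynamic group of 5 to 10 per direction, a full static group of 40, SDs from the plan's power section read as between-participant and equal in both OA groups, 3 trials per participant, and a two-sided 5% test. The logical point needs none of these assumptions. The consequence is confined to one additional analysis.

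**What to change.** Amend item 5 in four respects:

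1. Restate the Hypothesis 4 definition, so that the dynamic group is explicitly statically neutral and dynamically varus or valgus.
2. Compare varus with varus and valgus with valgus, separately.
3. Report each difference with its 95% CI whatever the p-value, and say that non-significance will not be read as similarity.
4. Claim similarity only if the interval lies within a margin that the investigators state and justify before the data are analysed; otherwise report the question as not resolved.

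This takes a few sentences and no new data. The cost is that the answer will often be unresolved: at n = 10 and SD 2.46 the half-width alone is about 1.75 degrees, so an interval would rarely fit inside a margin of that size. If the investigators prefer not to set a margin, the first three changes still remove the risk of a misleading conclusion, provided that no claim of similarity is made.
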